4.8 Screen failure procedures

Subjects who screen fail will be informed immediately. A copy of their consent form will still go into their electronic medical records (EMR) through EPIC. Any other paper source documents will be stored securely with other enrolled-patient information.

4.9 Qualifications of study team

The study team has Human Subject Protection and Good Clinical Practice training. The two psychiatrists on the team have been actively providing iTBS to adults for years. Questionnaires used in the study have been used by study team members in previous work both research and non-research related. Regarding NSSIB evaluations, study team received training from the psychology department by a Ph.D. and his graduate student who have studied NSSIB for years. The main study team (study coordinator and 2 M.D.'s) have been working together on multi-phase sponsor clinical trials for several years and have been trained in consent, questionnaires, and have clinical experience in diagnosing, intervention, and safety monitoring. The psychology department has also been invested in clinical research for years. Recruitment, questionnaires, and consent will be done by two M.D. psychiatrists and study coordinator. Confirmation of diagnosis, eligibility, physical and neurological exams, study intervention, and safety monitoring will be done by the two psychiatrists.

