4.2 Intervention/Treatment procedures (by visits)

- On the first treatment day: Prior to initiation of iTBS administration, the physician will establish 100% of motor threshold. iTBS will then be administered starting at 100% of motor threshold, increasing to 120% of motor threshold while adjusting the coil position to minimize side effects.
- The remaining 19 iTBS treatments: These will be delivered over a four week period, with five treatments delivered weekly by a UNC rTMS-trained physician Monday through Friday.
- General information about the entire treatment phase of study that is not visit specific: Each treatment will follow the iTBS protocols established by MagVenture, Inc. and treatment will be provided at 120% of motor threshold at all 20 treatment visits.
- Patients will undergo CDRS-R, HAM-D, and cognitive assessments once weekly during the treatment phase, starting on their fifth treatment day, and each week from that time point depending on which day of the week they start treatment.
- Patients will be assessed prior to every treatment for side effects or safety-related symptoms, as well as review of concomitant medication.

- Vitals will be taken prior to every treatment administration during all 20 treatment days. Weight will be obtained once per week during the treatment phase. Per investigator discretion, weight may be obtained at additional timepoints during the treatment phase or unscheduled visits to ensure safety of the subject.
- UDS and urine pregnancy tests can be done at any time due to investigator discretion for safety purposes. Pregnancy risk assessment will be documented at every visit for females of childbearing potential.

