5.0 STUDY EVALUATIONS AND MEASUREMENTS

5.1 Safety Evaluation

- **Variables that will be abstracted from medical charts:** General medical health and stability (current), concomitant medications, medical history, and diagnosis will be used to help determine patient eligibility.
- **Baseline evaluation:** Baseline will be done at screening while eligibility is determined. SCID-5, CDRS-R, HAM-D, MMSE, Trails B, List Generation, a semi-structured interview, and C-SSRS will be used for diagnosis of depression and baseline cognitive functioning.
 - SCID-5 – This is a structured interview to evaluate psychiatric diagnosis in children and adolescents. Interrater reliability ranges from .78-1 depending on the diagnosis. [23] This is a descriptive, yes/ no, diagnostic assessment that will only be used at screening.

- UDS and urine pregnancy tests for childbearing-capable participants will be performed at screening for eligibility purposes. Investigators will only repeat these tests as a discretionary basis if there is concern for pregnancy or unauthorized drug use that can cause the participant potential harm in conjunction with study participation.

- **How measurements will be taken:** Assessments will be done by a trained study staff in a private setting to ensure patient comfort and ability to answer questions. Various questionnaires will be used to measure baseline and efficacy, as listed above in section 5.1. These will be done at screening, and the end of each treatment week (4 times total during treatment phase), and again at each of the 3 follow-ups.

- **Rating scales, tests, psychological tools, laboratory evaluations, etc.** Assessments are described in section 5.2.

- **Safety evaluations** include vitals being monitored and a physical exam. Vitals will be monitored every visit. UDS and urine pregnancy test will be done at screening and any other time the investigator deems suspicion it is necessary for safety purposes. A physical exam will be done at screening and all follow up visits. Concomitant medication tracking and AE review will be done at every visit. Attention will also be placed on any change in medications or doses. Psychiatrists will evaluate safety through medical review of symptoms at each study visit and monitor treatment sessions. Additional questionnaires for safety and cognitive evaluation once per week during the treatment phase. Please see Appendix B for detailed information.

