- Missing Data and Protocol Violations: Data will be collected in multiple formats – on paper and later electronically. Paper data will include various scales and assessments. There will be two members of the investigation team during assessments and scale administration, which can assist with looking over the data. Paper documents will be labeled without any personal health information or other sensitive identifying information outside of the study team. These documents will be stored in a locked cabinet in a locked office. If there is any missing data, we will refer to the stored paper documents. If data continues to be missing, we are planning to mitigate selection bias by remarking clearly in our results and discussion that consideration must be given to this fact. Any protocol violations will be assessed by the Principal Investigator, will be submitted to the IRB, and a discussion will be had on how to proceed with the study.
- Other: For any missing data, rationale and documentation will be provided in the database (RedCap) and source documentation.

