Appendix B: TIME AND EVENT SCHEDULE

Time and Event Schedule	Screening	Weeks 1-4 Treatment*g					Follow up**		
Study tasks	V1 (1 wk period)	V2b ; V7, V12, V17	V3, V8, V13, V18	V4, V9, V14, V19	V5, V10, V15, V20	V6, V11, V16, V21	V22^c	V23^d	V24^d
Informed consent***	x								
CDRS-R***	x					x	x	x	x
HAM D ***	x					x	x	x	x
SCID-5***	x								
MSSE	x					x	x	x	x
Trails B	x					x	x	x	x
List Generation	x					x	x	x	x
NSSIB interview & SITBI	x					x	x	x	x
C-SSRS	x					x	x	x	x
UDS ^a	x								
Urine pregnancy test ^a	x								
Vitals (HR, RR, O ² , BP, temp, weight ^h)	x ^h	x	x	x	x	x ^h	x ^h	x ^h	x ^h
Physical exam ***	x						x	x	x
AE review ^h ***	x	x	x	x	x	x	x	x	x
Medication review ***	x	x	x	x	x	x	x	x	x
Satisfaction Questionnaire									x
Neurological exam***	x								
iTBS ^f ***		x	x	x	x	x			

Footnotes

a: Can be done anytime at investigator discretion for safety purposes, predose on any treatment day.

b: Treatment should start by the following business day, within 7 days of screening.

c: 1 week after last treatment.

d: 4 weeks after last treatment.

e: 12 weeks after last treatment.

f: First day of treatment will determine motor threshold

g: Will include change in pregnancy status (OHRE SOP 4801, re: verbal assessments for treatments w/o known teratogenic effects)

h. Weight also collected as planned timepoint – per investigator discretion can also be obtained at any time during participation

*: To be done Monday-Friday, can start any day of the week.

**: +/- 3 days

***: M.D. must be present and/or perform tasks.

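### The plan lets the psychiatrist who delivers a subject's iTBS also score that subject's CDRS-R and HAM-D, and it does not keep one rater per subject

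*Combined protocol and SAP*

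**What the plan says.** Section 4.9 divides the work among three people. On ratings: "Recruitment, questionnaires, and consent will be done by two M.D. psychiatrists and study coordinator". On treatment: "Confirmation of diagnosis, eligibility, physical and neurological exams, study intervention, and safety monitoring will be done by the two psychiatrists". Section 4.2 describes "five treatments delivered weekly by a UNC rTMS-trained physician Monday through Friday".

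Section 5.1 describes the rater only in general terms: "Assessments will be done by a trained study staff in a private setting". In Appendix B the CDRS-R, HAM-D and iTBS rows all carry the footnote "M.D. must be present and/or perform tasks", and all three are marked in the column for V6, V11, V16 and V21.

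Section 6.3, under missing data, adds: "There will be two members of the investigation team during assessments and scale administration, which can assist with looking over the data". Section 10.4 has scores verified by at least two people. Section 3.2 marks blinding as not applicable.

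Section 6.1 defines the primary endpoint as the difference in CDRS-R and HAM-D scores divided by the standard deviation.

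**The concern.** Both primary scales depend on a clinician's judgement. Section 5.2 describes the CDRS-R as a semi-structured interview in which 3 of the 17 scored items rest on observation. A rater who has just given the treatment has a natural reason to expect improvement. In a controlled trial with raters unaware of allocation, much of that expectation would cancel between arms. Here there is no second arm, so whatever enters the scores stays in the estimate.

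The plan also does not keep one rater per subject. If one person scores baseline and another scores a later visit, any difference in how the two score becomes part of the recorded change.

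The effect-size estimate is at stake. Sections 3.3 and 6.4 intend these data to support a larger grant application, so an inflated or noisier estimate would be carried into the planning of the next study.

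**Working it through.** The plan gives no figure to reproduce here: it states no alpha, power, SD or expected effect. The check compares the relevant sections, counts the rating visits, and works through how the rater enters the endpoint.

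1. **Who may do what.**
   - Ratings: either psychiatrist or the coordinator (Section 4.9); any trained staff (Section 5.1); a physician present or performing (Appendix B).
   - iTBS: the two psychiatrists (Section 4.9); a trained physician (Section 4.2); a physician present or performing (Appendix B).
   - Both psychiatrists are on both lists. The coordinator is on the rating list only.

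2. **How often the overlap can occur.** Section 5.1 and Appendix B give 1 screening + 4 treatment-phase + 3 follow-up = 8 rating visits per subject, of which 8 − 1 = 7 are after baseline. As a check on the schedule, 1 screening + 20 treatment + 3 follow-up = 24 visits, which agrees with Section 3.3. The 4 treatment-phase ratings fall on iTBS days, when one physician could both treat and rate. Over 5 subjects that is 5 × 4 = 20 of the 5 × 8 = 40 rating visits. At the 3 follow-up visits no iTBS is given, but the rater could still be the person who delivered it.

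3. **Whether anything prevents it.** The two-person attendance in Section 6.3 has the stated purpose of looking over the data. The verification in Section 10.4 checks recorded scores. Neither concerns who forms the rating. Section 6.3 concedes that improvement may not be due to treatment, which is about the cause of a true change. It does not address whether the recorded change is itself accurate.

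4. **How the rater enters the endpoint.** Write the recorded score at visit t as true score + rater's habitual offset r(t) + expectancy shift e(t). Then:

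   recorded change = true change + [r(t) − r(0)] + [e(t) − e(0)].

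   - With the same rater and a stable offset, r(t) − r(0) = 0. With different raters it need not be zero, and it adds noise.
   - If expectancy lowers post-baseline scores by a constant b points, recorded improvement rises by b and the Section 6.1 effect size rises by b/SD. This does not depend on the number of subjects, and the confidence intervals promised in Section 6.4 would simply be centred on the shifted value.

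5. **Illustration only.** The documents give neither b nor SD. Assuming b = 2 to 5 points and SD = 8 to 15 points, the smallest ratio is 2/15 = 0.13 and the largest is 5/8 = 0.63. These figures describe the whole assumed shift. How much of it a separate rater would remove is unknown.

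**The case against.** The best case against runs as follows. This is an open-label pilot in five subjects. Section 6.3 already says that improvement may not be attributable to treatment and that a larger, possibly sham-controlled, study would be indicated. Section 6.4 disclaims significance, and the Aim 3 feasibility criterion uses no depression score. A separate rater would still know that treatment is active and would remain a colleague on the same project. Strict separation would also bar one psychiatrist from covering the other's sessions. Missed sessions count towards the 20% provision in Sections 4.7 and 8.0 and towards the 15 of 20 sessions in Aim 3.

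Much of this stands. It limits the benefit, and it rules out any remedy that would put sessions at risk. It does not remove the point, because open label means that the rater knows the treatment, not that the rater must have given it. The HAM-D interrater reliability of 0.97 to 0.98 in Section 5.2 suggests that noise from changing raters may be small on that scale. It does not speak to an expectation that raters share, and Section 5.2 gives no such figure for the CDRS-R.

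A reader might infer four stronger things that the documents do not support:
- *That the treating psychiatrists will be the raters.* The coordinator may rate, so the overlap is permitted, not stated.
- *That two psychiatrists attend every assessment.* Section 6.3 says "There will be two members of the investigation team during assessments and scale administration", which one psychiatrist and the coordinator would satisfy.
- *That anchoring on earlier scores always favours improvement.* Anchoring pulls a new score towards the last one. Early on this would shrink apparent improvement; later it could make a gain look more lasting.
- *That earlier scores should be kept from the rater.* The documents do not say whether raters see them. In a three-person core team that also verifies scores (Section 10.4) and monitors response (Section 10.1), withholding them would be hard to sustain.

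**Conclusion.** The point holds in a limited form. Sections 4.9 and 5.1 and Appendix B allow a subject's treating psychiatrist to score the primary outcomes, and allow the rater to change between visits. With an uncontrolled within-subject endpoint, rater expectancy would tend to inflate the change, and changing raters would add noise. The direction for expectancy is a judgement about how raters usually behave, not something the documents show. The size is not estimable from them, and the 0.13 to 0.63 range rests wholly on assumed values.

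This is a cheap improvement. It changes no sample size, power or feasibility criterion, and it does not undermine the pilot.

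**What to change.** State in Sections 4.9 and 5.1 that:
- for each subject, one designated rater from the existing team who does not deliver that subject's iTBS scores CDRS-R and HAM-D at all 8 rating visits where possible;
- this rater is either the other psychiatrist, or the trained coordinator with a physician present, as the Appendix B footnote allows;
- the rater and the treater are recorded at each visit;
- the second psychiatrist may cover sessions when needed, so that the rating rule causes no missed session;
- any rating made by someone who had treated the subject is identified in the report.

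The assignment must be written down per subject, because if both psychiatrists share a subject's 20 sessions, neither is a non-treating rater. Naming the coordinator avoids that problem, since Section 4.9 gives the coordinator no role in delivering iTBS.

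No new staff are needed. The cost is less flexible rostering, mainly on the 4 treatment-phase rating days per subject. Section 3.3 expects subjects to be treated one at a time, which eases this. The rater will still know that treatment is open label, so the change reduces bias without removing it.

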5.0 STUDY EVALUATIONS AND MEASUREMENTS

5.1 Safety Evaluation

- **Variables that will be abstracted from medical charts:** General medical health and stability (current), concomitant medications, medical history, and diagnosis will be used to help determine patient eligibility.
- **Baseline evaluation:** Baseline will be done at screening while eligibility is determined. SCID-5, CDRS-R, HAM-D, MMSE, Trails B, List Generation, a semi-structured interview, and C-SSRS will be used for diagnosis of depression and baseline cognitive functioning.
 - SCID-5 – This is a structured interview to evaluate psychiatric diagnosis in children and adolescents. Interrater reliability ranges from .78-1 depending on the diagnosis. [23] This is a descriptive, yes/ no, diagnostic assessment that will only be used at screening.

- UDS and urine pregnancy tests for childbearing-capable participants will be performed at screening for eligibility purposes. Investigators will only repeat these tests as a discretionary basis if there is concern for pregnancy or unauthorized drug use that can cause the participant potential harm in conjunction with study participation.

- **How measurements will be taken:** Assessments will be done by a trained study staff in a private setting to ensure patient comfort and ability to answer questions. Various questionnaires will be used to measure baseline and efficacy, as listed above in section 5.1. These will be done at screening, and the end of each treatment week (4 times total during treatment phase), and again at each of the 3 follow-ups.

- **Rating scales, tests, psychological tools, laboratory evaluations, etc.** Assessments are described in section 5.2.

- **Safety evaluations** include vitals being monitored and a physical exam. Vitals will be monitored every visit. UDS and urine pregnancy test will be done at screening and any other time the investigator deems suspicion it is necessary for safety purposes. A physical exam will be done at screening and all follow up visits. Concomitant medication tracking and AE review will be done at every visit. Attention will also be placed on any change in medications or doses. Psychiatrists will evaluate safety through medical review of symptoms at each study visit and monitor treatment sessions. Additional questionnaires for safety and cognitive evaluation once per week during the treatment phase. Please see Appendix B for detailed information.

- Columbia-Suicide Severity Rating Scale (C-SSRS) – C-SSRS is a tool widely used in clinical settings to assess suicidality. A large problem before the scale's existence was a lack of uniformity among assessing suicidality. C-SSRS was created to address this measuring four different constructs. These constructs are severity of ideation, intensity of ideation, behavior subscale, and lethality subscale. C-SSRS is endorsed and recommended by multiple health and mental health related organizations. C-SSRS is an effective assessment tool for clinical and research environments. [25] This is a descriptive and yes/no assessment.

- Cognitive assessments:

Mini-Mental Status Exam (MMSE): MMSE is a tool used to assess cognitive function. It consists of 30 items assessing orientation to time, orientation to place, attention and calculation, registration, recall, language, repetition, and complex commands. While used primarily for assessment of dementia in older adults, MMSE is useful in assessing and screening intellectual disabilities in children and adolescents. Preliminary studies found and concluded that MMSE could be used as a tool to assess cognitive function of children ages 4 and older. [26] This is a scored assessment.

Trail Making Test Part B (TMT-B): TMT (Trails Making Test) is another tool used to assess cognitive function. The test consists of two parts. Part A consists of connecting the dots together in sequential order based on numbers (1,2,3...). Part B consists of the same idea but uses and alternates both letters and numbers (1,A,2,B,3,C...) with the goal of connecting the dots in sequential order. TMT has a number of studies that supports its effectiveness and depicts its ability to differentiate between children with achievement deficits and learning disabilities from their normally developing peers. Trails B has been found to be more sensitive to these differences than Trails A. [27] This is a scored assessment.

List Generation: This assessment determines the ability for one to recall as many items as possible in a given category. This study will utilize “animal names”, where subjects are to recall at least 14 animals with a 60 second period. This is a scored assessment.

5.2 Efficacy Evaluation

Children’s Depression Rating Scale Revised (CDRS-R) – This is one of the most commonly used assessment tools for pediatrics when identifying depression. It assesses symptom severity and can be administered filtered or unfiltered (in context of mood disorder or not). [28] It is a semi structured interview scale. 17 items are scored, with 3 of these 17 being made from observation versus verbal response [28]. This will evaluate overall wellness to determine efficacy of treatment, measuring sleep, appetite, socialization, school/work functioning, and overall wellness. This is a scaled and scored assessment and is filtered.

Hamilton Depression Rating Scale (HAM-D) – This is the most widely used tool to evaluate depression. Interrater reliability is high at 0.97-0.98. It is easily administered and measures severity of depression. It is considered the “gold standard” when assessing depression. There are 21 items to score however only the first 17 are actually totaled, each question has a scaled answer. [29] The HAM-D used in this protocol is the same tool used for routine clinical services in the Department of Psychiatry at UNC. This will also evaluate overall wellness to determine efficacy of treatment, measuring sleep, appetite, socialization, school/work functioning, and overall wellness. This is a scaled and scored assessment.

SITBI (Self-Injurious Thoughts and Behaviors Interview) short form & semi structured interview – Self-injurious thoughts and behaviors, lifetime and past month will be assessed using the Self-Injurious Thoughts and Behaviors Interview (SITBI) short form, a clinician-administered interview (3-10 min) that assesses the presence, frequency, severity, age-of-onset, and other characteristics of a broad range of self-injurious thoughts and behaviors. The SITBI has strong convergent validity, inter-rater reliability ($K = .90$), and test-retest reliability ($K = .70$). [30] It is a comprehensive assessment that is recommended for use in clinical and research settings. [30] This is a descriptive, yes/no assessment.

Other: Patient/Caregiver Satisfaction questionnaire: This is an original, brief questionnaire using scaled and open ended questions that is self-reported. This will gather information on what the participants found helpful and what could be improved for future studies. This questionnaire was created in collaboration and upon request of the funding source Center for Health Innovation.

